**Test Product, Dosage and Mode of Administration:**

Crenolanib besylate will be taken at a starting dose of 100 mg TID, orally. Patient, nursing or research staff will complete documentation to record the date, time and amount (number of tablets) of crenolanib taken.

**Drug Information:**

Crenolanib besylate will be provided in 100 mg and/or 20 mg tablets by Arog Pharmaceuticals, Inc.

**Study Design:**

Patients will initially be enrolled to the safety phase of the study. During the safety phase, patients will be enrolled to either cohort A: cytarabine/daunorubicin or cohort B: cytarabine/idarubicin. Each cohort will enroll independently and patients will be treated with crenolanib following either cytarabine/daunorubicin or cytarabine/idarubicin.

Once safety of adding crenolanib to cytarabine/daunorubicin and cytarabine/idarubicin has been established, an expansion phase of an additional 72 patients will be treated with standard 7+3 (either cytarabine/daunorubicin or with cytarabine/idarubicin, per physician's discretion) induction chemotherapy followed by crenolanib.

Per physician's discretion, patients may receive up to 2 cycles of the same induction therapy. Following induction, eligible patients can receive up to four cycles of consolidation with HiDAC followed by crenolanib. Following either

induction or consolidation, eligible patients may receive maintenance therapy with crenolanib up to an additional 12 cycles.

Eligible patients should receive allogeneic stem cell transplant following induction and/or consolidation with HiDAC. Those who have received transplant may receive maintenance therapy with crenolanib following transplant.

**Planned Duration of Treatment:**

If patients receive all available therapy options, patients may stay on trial for approximately 20 months. Information for survival and disease status (until progression of disease) on patients who have discontinued study drug for any reason should be obtained at least every 6 months for a maximum of 24 months or until the end of the study, whichever is later.

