### 3.2. Study Synopsis

**Title of Study:** A Study of Crenolanib and Chemotherapy in Patients with Newly Diagnosed Acute Myeloid Leukemia with FLT3 Activating Mutations

**Number of Planned Subjects:** 120

*Approximately 48 patients will be enrolled into two cohorts during an initial safety phase:*

- Cohort A: 24 patients receiving cytarabine/daunorubicin followed by crenolanib
- Cohort B: 24 patients receiving cytarabine/idarubicin followed by crenolanib

Once safety of adding crenolanib to cytarabine/daunorubicin and cytarabine/idarubicin has been established, an expansion phase of 72 additional patients will be treated with either cytarabine/daunorubicin or with cytarabine/idarubicin induction chemotherapy followed by crenolanib to further assess the safety and clinical benefit of the combination.

**Length of Study:** 2-3 years

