#### 4. ABBREVIATIONS AND DEFINITIONS

Adverse Event (AE)	Any untoward medical occurrence in a patient or clinical investigation subject administered a pharmaceutical product and which does not necessarily have a causal relationship with this treatment. An adverse event can therefore be any unfavorable and unintended sign (including an abnormal laboratory finding), symptom, or disease temporally occurring during the use of a medicinal (investigational) product, whether or not related to the medicinal (investigational) product.
Audit	A systematic and independent examination of the trial-related activities and documents to determine whether the evaluated trial-related activities were conducted, and the data were recorded, analyzed, and accurately reported according to the protocol, applicable standard operating procedures (SOPs), good clinical practice (GCP), and the applicable regulatory requirement(s).
Compliance	Adherence to all the trial-related requirements, good clinical practice (GCP) requirements, and the applicable regulatory requirements.
Complaint	A complaint is any written, electronic, or oral communication that alleges deficiencies related to the identity, quality, purity, durability, reliability, safety or effectiveness, or performance of a drug or drug delivery system.
Confirmation	A process used to confirm that laboratory test results meet the quality requirements defined by the laboratory generating the data and that AROG is confident that results are accurate. Confirmation will either occur immediately after initial testing or will require that samples be held to be retested at some defined time point, depending on the steps required to obtain confirmed results.
Case Report Form (CRF)	Sometimes referred to as clinical report form: a printed or electronic form for recording study participants' data during a clinical study, as required by the protocol.
Consent	The act of obtaining informed consent for participation in a clinical trial from patients deemed eligible or potentially eligible to participate in the clinical trial. [Patients/Subjects] entered into a trial are those who sign the informed consent document directly or through their legally acceptable representatives.
End of Study (trial)	The date of the last visit or last scheduled procedure shown in the Study Schedule for the last active subject in the study.

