**13.2. Safety monitoring during the initial safety phase**

Adverse events, as defined in Section 14.1, will be monitored during the treatment and post-treatment follow up periods. Adverse events will be monitored on a continuous basis by the sponsor.

The Protocol Safety Committee will review safety data from this trial on a periodic basis. The committee also will monitor the safety outcomes listed below for purposes of determining if enrollment in one or both cohorts should continue or be halted. Within each cohort, up to 6 patients will be initially enrolled. For the first 6 patients, patients will be enrolled in a sequential manner such that no more than 3 patients are within 30 days of starting induction 1 therapy. Enrollment will be halted within a cohort if an apparent increase is observed in the occurrence of one or more of the following outcomes:

- Early mortality due to any cause
- Expected, non-hematologic, crenolanib-related toxicity (CTCAE Grade 4)
- Unexpected, non-hematologic, crenolanib-related toxicity (CTCAE Grade 4)

The criteria used to determine if enrollment will be halted are described in sections 13.2.1, 13.2.2 and 13.3.3.

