### **13.9. Criteria for End of Study**

This study will be considered complete following the data cut-off date for the final analysis. Documentation of the data cut-off will be included in the master study file. After the final analysis, if subjects are continuing to benefit from study treatment, they will be allowed to continue receiving study treatment for up to one year as part of planned maintenance. Patient is considered “off therapy” when study drug stops for any reason and crenolanib therapy is not continued. Patient is considered “off study” after completion of the 30-day safety follow up, 2 year follow-up period or upon death or upon start of a new therapy, whichever comes first.

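### The stated study length of 2-3 years cannot hold about 20 months on trial plus 24 months of follow-up, and conflicting follow-up rules leave the maturity of OS, RFS and remission duration unassured

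*Combined protocol and SAP*

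**What the plan says.** - **Length.** The synopsis (Section 3.2) states "Length of Study: 2-3 years".
- **Time on trial.** Under Planned Duration of Treatment: "If patients receive all available therapy options, patients may stay on trial for approximately 20 months".
- **Follow-up.** The same paragraph has survival and disease status collected, for patients who have stopped study drug, "at least every 6 months for a maximum of 24 months or until the end of the study, whichever is later". It does not say from which date the 24 months runs.
- **End of study, Section 4.** "The date of the last visit or last scheduled procedure shown in the Study Schedule for the last active subject in the study".
- **End of study, Section 13.9.** "This study will be considered complete following the data cut-off date for the final analysis". No date, event count or minimum follow-up is attached. A patient leaves the study at the first of several events, the list being the 30-day safety follow-up and then "2 year follow-up period or upon death or upon start of a new therapy, whichever comes first".
- **After relapse or refractory disease, Section 7.4.1.** Crenolanib stops, but the patient is still followed for survival.
- **Use of the data.** OS, remission duration and RFS are secondary objectives (Section 6.2), summarised descriptively by Kaplan-Meier and cumulative incidence (Section 13.1.1). No landmark time or target number of events is given.

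**The concern.** A study length shorter than one patient's treatment plus follow-up means that something in the plan will not happen, and the plan does not say what. If the sponsor holds to 2-3 years, follow-up of the patients who stay longest on treatment is what gets cut.

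The off-study rule raises a separate problem that does not depend on study length. A patient who starts a new therapy after relapse is usually at higher risk of death than one who does not. Censoring OS at that point makes the censoring informative, and a Kaplan-Meier curve would then tend to look too favourable. The documents give no relapse or salvage rates from which to size that bias.

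**Working it through.** **1. Reproduce the 20 months.** Inputs: up to 2 inductions, 4 consolidations and 12 maintenance cycles of 28 days (Sections 1 and 8.2); at least 30 days between transplant and maintenance (Section 8.2.3). Induction and consolidation cycle lengths are not fixed. I assume 28 to 42 days, the upper value being the Day 42 marrow in Section 8.2.1.

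- Shortest: 2×28 + 4×28 + 12×28 = 504 days; 504 / 30.44 = 16.6 months.
- Longest: 2×42 + 4×42 + 12×28 + 30 = 618 days; 618 / 30.44 = 20.3 months.

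The plan's figure of about 20 months reproduces at the upper end.

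**2. Add follow-up.** Counting from drug discontinuation, the natural reading of the synopsis: 20 + 24 = 44 months. The excess is 44 − 36 = 8 months over the upper bound and 44 − 24 = 20 months over the lower. Using the shortest course instead, 16.6 + 24 = 40.6 months, still above 36. A patient enrolled on the first day of a 36-month study could complete 24 months off drug only if on trial for no more than 36 − 24 = 12 months.

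**3. Add accrual.** No accrual period is stated. It cannot be zero, because in the first six patients of each cohort "no more than 3 patients are within 30 days of starting induction 1 therapy" is allowed. With assumed accrual of 12, 18 or 24 months, the span until a last-enrolled full-course patient completes follow-up is 44 + 12 = 56, 44 + 18 = 62 or 44 + 24 = 68 months.

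**4. Set the follow-up rules side by side.**

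- The synopsis calls 24 months a maximum, yet its later-of clause makes 24 months a floor.
- Section 13.9 uses an earliest-of rule. Read literally, the 30-day safety follow-up always comes before the 2-year limit, so the 2-year follow-up could never be completed. Even if the 30 days concerns safety data only, a new therapy still ends participation, against Section 7.4.1.
- Section 4 depends on the Study Schedule. As supplied in Appendix IV, that schedule stops at progression or completion of study and lists no survival contacts. Section 13.9 ends the study at the data cut-off instead.

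**5. What a cut-off at the stated length would leave.** For a cut-off at month L and uniform accrual over A months (assumed), potential follow-up from entry is L − A for the last patient and L − A/2 at the median, and a share (L − 24)/A, limited to 0-100%, has at least 24 months. For illustration only, with exponential OS and λ = ln 2 / median, expected deaths are 120 × [1 − (e^(−λ(L−A)) − e^(−λL)) / (λA)].

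| L | A | Last patient | Median | At least 24 months | Deaths of 120 (OS median 12 / 24 / 36 months) |
|---|---|---|---|---|---|
| 36 | 12 | 24 | 30 | 100% | 98 / 69 / 53 |
| 36 | 18 | 18 | 27 | 67% | 94 / 64 / 48 |
| 36 | 24 | 12 | 24 | 50% | 88 / 59 / 44 |
| 36 | 30 | 6 | 21 | 40% | 80 / 53 / 39 |
| 24 | 12 | 12 | 18 | 0% | 77 / 48 / 35 |
| 24 | 18 | 6 | 15 | 0% | 67 / 41 / 30 |

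Maturity therefore ranges from adequate to poor, depending on accrual and cut-off, neither of which the plan fixes.

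**The case against.** The strongest reply is that the length is a synopsis line that triggers no analysis. Twenty months is a maximum: patients who are refractory, relapse or stop early need less time, and they supply off-drug survival data early. Nothing ties the cut-off to month 24 or 36, and an open cut-off is not an early one. Kaplan-Meier handles administrative censoring, and these endpoints are secondary and descriptive. If the 24 months ran from entry, a 36-month study would fit with accrual within 12 months. Section 13.1 announces a separate SAP, not among the text supplied, which may set a cut-off.

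Most of this stands, and it limits the point. A reader might infer that OS, RFS and remission duration would be read before they can be observed. The documents do not support that, as the table in the working shows.

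A reader might also infer that no expansion patient could finish treatment within 24 months, by taking the expansion to open at about day 210. That date needs a 60-day reading of patients 13-24, which Sections 13.2.1 to 13.2.3 do not require. Even from day 210, a 504-day course ends at day 714, or 23.5 months.

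Nor does Section 13.9 expect patients to have a year of maintenance left after the final analysis. It conditionally permits continued treatment.

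The reply does not remove the contradiction between the stated length and the plan's own schedule, or the conflict among the follow-up rules. A separate SAP could set a cut-off but would not correct the protocol text.

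**Conclusion.** The point holds as an internal inconsistency with a real but bounded consequence. The stated length is 8 to 20 months shorter than a full course plus follow-up, before accrual. This assumes that the 24 months runs from drug discontinuation. It does not depend on the exact treatment length, since the shortest rebuilt course also exceeds 36 months.

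The end-of-follow-up rules in the synopsis and Sections 4, 7.4.1 and 13.9 cannot all be applied. The off-study rule is the more serious part, because it could censor OS at relapse therapy whatever the study length. What follows is that the maturity of OS, RFS and remission duration is not assured. It does not follow that they are unobservable or that an early reading is forced. The induction-response endpoint is unaffected.

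**What to change.** 1. State the accrual period, and restate the length as that period plus up to about 44 months. If 2-3 years is kept, limit OS and RFS reporting to a fixed horizon from start of induction that every patient can reach. With a 36-month study, that horizon is 24, 18 or 12 months for accrual of 12, 18 or 24 months.
2. State whether the 24 months runs from drug discontinuation or from entry, and delete either the word *maximum* or the later-of clause.
3. Use one end-of-study definition in the synopsis, Section 4 and Section 13.9.
4. Reconcile the off-study rule in Section 13.9 with the synopsis and Section 7.4.1, so that survival follow-up continues after relapse or new therapy.
5. In Section 13.9, tie the final time-to-event cut-off to a stated minimum follow-up of the last patient, and allow the response analysis earlier. The minimum is the sponsor's choice. A full 24 months off drug for the last patient is one option, but it keeps sites and database open for the 56 to 68 months shown above.

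The cost is a longer, less favourable stated length and a later final OS and RFS report, with the sites and database kept open to match. No patients are added, and the synopsis already requires the follow-up contacts.

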**Statistical Plan:**

During the initial safety phase, there will be two cohorts (based on chemotherapy regimen). Each cohort will enroll independently. To confirm the safety of each combination (cytarabine/daunorubicin with crenolanib and cytarabine/idarubicin with crenolanib), approximately 24 patients will be enrolled onto each cohort, if early stopping criteria are not met. Following analysis of the initial safety phase, an expansion phase of an additional 72 patients will be initiated to further assess safety and clinical benefit of this combination.

**Safety analysis:**

During the initial safety phase, twelve patients will be enrolled onto each cohort and if the early stopping rule criterion are not met than approximately 12 additional patients will be enrolled onto each cohort. Safety monitoring will be performed separately for each cohort and enrollment will be halted within a cohort if stopping rules are met for early mortality due to any cause, increase in expected non-hematologic crenolanib-related grade 4 adverse events, or any unexpected non-hematologic crenolanib-related grade 4 adverse events.

Stopping rules during the initial safety phase are the following: If the observed mortality rate exceeds 10 % and 20% at day 30 and 60, respectively, enrollment will be halted pending Protocol Safety Committee review. If an observed increase of expected non-hematologic crenolanib-related grade 4 adverse events exceeds 20% during the first 60 days of treatment further enrollment will be halted pending Protocol Safety Committee review. If an observed increase of unexpected non-hematologic crenolanib-related grade 4 adverse event exceeds 15% during the first 60 days of treatment further enrollment will be halted pending Protocol Safety Committee review.

During the expansion phase, safety monitoring will be performed for the entire per protocol patient population (defined as those who receive at least one dose of study drug) and in a separate analysis dictated by chemotherapy agent used.

**Response rate analysis:**

This study will enroll approximately 120 patients with the following confidence intervals based on projected response rate. A response rate of 90% will have a 95% CI of  $\pm 5\%$ . That is to say that if we treat 120 patients and observe a 90% response rate, we are 95% sure that the true response rate is between 85% to 95%.

**Analysis method:**

Descriptive statistics will be used to summarize the safety and efficacy data for this study. Categorical data will be summarized by number and percentage of patients in each category. Time – to – event endpoints will be summarized using the cumulative incidence and Kaplan-Meier methodology.

#### 4. ABBREVIATIONS AND DEFINITIONS

Adverse Event (AE)	Any untoward medical occurrence in a patient or clinical investigation subject administered a pharmaceutical product and which does not necessarily have a causal relationship with this treatment. An adverse event can therefore be any unfavorable and unintended sign (including an abnormal laboratory finding), symptom, or disease temporally occurring during the use of a medicinal (investigational) product, whether or not related to the medicinal (investigational) product.
Audit	A systematic and independent examination of the trial-related activities and documents to determine whether the evaluated trial-related activities were conducted, and the data were recorded, analyzed, and accurately reported according to the protocol, applicable standard operating procedures (SOPs), good clinical practice (GCP), and the applicable regulatory requirement(s).
Compliance	Adherence to all the trial-related requirements, good clinical practice (GCP) requirements, and the applicable regulatory requirements.
Complaint	A complaint is any written, electronic, or oral communication that alleges deficiencies related to the identity, quality, purity, durability, reliability, safety or effectiveness, or performance of a drug or drug delivery system.
Confirmation	A process used to confirm that laboratory test results meet the quality requirements defined by the laboratory generating the data and that AROG is confident that results are accurate. Confirmation will either occur immediately after initial testing or will require that samples be held to be retested at some defined time point, depending on the steps required to obtain confirmed results.
Case Report Form (CRF)	Sometimes referred to as clinical report form: a printed or electronic form for recording study participants' data during a clinical study, as required by the protocol.
Consent	The act of obtaining informed consent for participation in a clinical trial from patients deemed eligible or potentially eligible to participate in the clinical trial. [Patients/Subjects] entered into a trial are those who sign the informed consent document directly or through their legally acceptable representatives.
End of Study (trial)	The date of the last visit or last scheduled procedure shown in the Study Schedule for the last active subject in the study.
Enroll	The act of assigning a patient to a treatment. Patients who are enrolled in the trial are those who have been assigned to a treatment.
Investigator	A person responsible for the conduct of the clinical trial at a trial site. If a trial is conducted by a team of individuals at a trial site, the investigator is the responsible leader of the team and may be called the principal investigator.
Institutional Review Board/Ethical Review Board (IRB/ERB)	A board or committee (institutional, regional, or national) composed of medical and nonmedical members whose responsibility is to verify that the safety, welfare, and human rights of the patients participating in a clinical trial are protected.

Legal Representative	An individual, judicial, or other body authorized under applicable law to consent on behalf of a prospective patient, to the patient's participation in the clinical trial.
Patient	A study participant who has the disease or condition for which the investigational product is targeted.
Screen	The act of determining if an individual meets minimum requirements to become part of a pool of potential candidates for participation in a clinical trial. In this study, screening involves invasive or diagnostic procedures and/or tests (for example, radiology and blood draws). For this type of screening, informed consent for these screening procedures and/or tests shall be obtained.
Treatment-Emergent Adverse Event (TEAE)	Any untoward medical occurrence that either occurs or worsens at any time after treatment baseline and which does not necessarily have to have a causal relationship with this treatment (also called treatment-emergent signs and symptoms [TESS]).
ALT	alanine aminotransferase
AML	acute myeloid leukemia
Ara-C	cytarabine
ASCO	American society of clinical oncology
AST	aspartate aminotransferase
BMA	bone marrow aspiration
BUN	blood urea nitrogen
CALGB	cancer and leukemia group b
CBC	complete blood count
CIV	continuous intravenous therapy
CNS	Central nervous system
CR	complete response
CRi	complete remission with incomplete blood count recovery
CYP3A4	Cytochrome P450 3A4
DNA	deoxyribonucleic acid
ECOG -PS	Eastern Cooperative Oncology Group performance status
EFS	Event free survival
EKG	Electrocardiogram
FLT3	FMS-like Tyrosine Kinase 3
GCP	good clinical practice
GVHD	Graft versus host disease
HI	Hematologic improvement
HiDAC	High dose cytarabine
HSCT	Hematologic stem cell transplant
IC50	Half maximal inhibitory concentration
ICD	informed consent document
ICH	International Conference on Harmonization
IRB	Internal review board
ITD	internal tandem duplication
IV	Intravenous therapy
Kd	Dissociation constant
KIT	Stem cell growth factor receptor

---

LDH	Lactate dehydrogenase
MDS	Myelodysplastic syndrome
NCI CTCAE	National Cancer Institute Common Terminology Criteria for Adverse Events, Version 4.03
NYHA	New York Heart Association
OS	Overall survival
PD	progressive disease
PIA	Pharmacologic inhibitory assay
PK	Pharmacokinetics
PO	By mouth
PR	Partial response
RFS	relapse-free survival
SAE	Serious adverse event
TID	Three times a day
TKD	tyrosine kinase domain
TKI	tyrosine kinase inhibitor
ULN	upper limit of normal
UPIN	Unique patient identification number
WBC	White blood count
WOCBP	Woman of child bearing potential

